cRCT	Cluster-Randomized Controlled Trial
CRF	Case Report Form
Eawag	Swiss Federal Institute of Aquatic Science and Technology
EPFL	Ecole Polytechnique Fédérale de Lausanne
FACET WINS	Facility Evaluation Tool for WASH in Schools
FGD	Focus Group Discussion
FHNW	Fachhochschule Nordwestschweiz
H4H	Hands4Health
HRO	Ordinance of Human Research with the Exception of Clinical Trial (Switzerland)
ICF	Informed Consent Form
IDP	Internally Displaced People
IEC	Independent Ethics Committee
ICP	Infection Prevention and Control
JMP	Joint Monitoring Programme
KII	Key Informant Interview
LDCs	Least Developed Countries
LMIC	Low and Middle-Income Country
MCI	Multi-component intervention
NGO	Non-Governmental Organization
ODK	Open Data Kit
RANAS	Risk, Attitude, Norm, Ability and Self-regulation
SDC	Swiss Agency for Development and Cooperation
SDG	Sustainable Development Goal
Swiss TPH	Swiss Tropical and Public Health Institute
Tdh	Terre des hommes
ToA	Theory Of Action
ToC	Theory Of Change
UNICEF	United Nations Children's Fund

WASH	Water, Sanitation and Hygiene
WHO	World Health Organization

IV. Synopsis

Project Leader	[name] [name]
Study Title	hands4health: Hand hygiene, water quality and sanitation in schools not connected to functional water supply system: a cluster-randomized controlled trial in Nigeria and Palestine
Short Title/Study ID	Hand hygiene intervention in schools- H4H
Protocol Version and Date	Version 1.0, 02.06.2023
Study Category with Rationale	Non-clinical study, risk category A: no drugs are being tested, and only hand-rinse samples are being taken
Background and Rationale	
Despite the effectiveness of hand hygiene in reducing the transmission of infectious diseases – as demonstrated by the COVID-19 pandemic – 2.3 billion people – primarily located in low- and middle-income countries (LMICs) – are exposed to increased risk of infectious diseases as a result of lack of access to water and hygiene services. Improving hand hygiene is most challenging in humanitarian contexts, where challenges in water availability and quality in combination with overcrowded conditions often limit access to sanitation and hygiene services. Schools are one of the most critical places where adequate water, sanitation and hygiene (WASH) should be provided in such settings.
 
Against this background, the Hand4Health (H4H) project will implement a multicomponent intervention (MCI) designed to improve hand hygiene and access to water for students in schools not connected to functional water systems in Nigeria and Palestine by providing them with a sustainable handwashing system and a package of systematic handwashing-behaviour change activities.

Objective(s)	
Primary objective: Evaluate the effects of the H4H multi-component intervention (MCI) package on hand hygiene of primary school students in Nigeria and Palestine.
 
Secondary objectives:
 
 1) Evaluate the effects of the H4H MCI package on the well-being of primary school students in Nigeria and Palestine 2) Assess the impact of the H4H MCI package on hygiene-related risks, attitudes, norms, abilities and self-regulation (RANAS) behavioural factors of primary school students in Nigeria and Palestine 3) Assess the effect of the H4H MCI package on absenteeism incidence and hygiene-related health outcomes of primary school students in Nigeria and Palestine 4) Explore the associations of personal, physical and social contextual factors with hand hygiene and the well-being of primary school students in Palestine 5) Explore the perceived impacts of the H4H MCI package on the health and well-being of primary school students in Nigeria and Palestine

Primary Endpoint Secondary Endpoints	
The primary endpoint of this study will be good handwashing practice defined as students who wash their hands with water and soap before eating assessed by structured handwashing observations.
 
The secondary endpoints are:
 
 Good handwashing practice defined as students who wash their hands with water and soap after using the toilet assessed by structured handwashing observation Self-reported handwashing practice answered for two critical events; before eating and after using the toilet, on a Likert scale ranging from almost never to almost always. The well-being of students assessed by KINDL tool Number of total coliforms and E.coli colony-forming units (CFUs) per hand before handwashing. Hygiene-related health outcomes and absenteeism incidence. The health outcomes will be reassessed with local experts in the country to assure feasibility before the start of the intervention.
Study Design	
Overall project: Multi-center cluster-randomized controlled trial (cRCT) design.
 
Module 1-3 will be repeated three times within the cRCT at baseline, three months post-intervention and at endline. Module 4 data collection will take place in both study arms longitudinally starting after the intervention has been implemented. Module 5 will be a self-reported survey administered for the parents of the students included in the study at baseline in Palestine. Module 6 and 7 are qualitative focus group discussions (FGDs) and interviews and will take place after the second round of data collection in Modules 1-3.

Inclusion/Exclusion Criteria	
Study participants are primary school students aged 10-12 years attending eligible schools that were selected to be included in this study.
 
Inclusion criteria Modules 1-4: Schools were selected based on accessibility for the study teams, not having a water source directly connected to the building of the school, having primary grades (5th-7th), having ≤ 7000 students and being impacted by conflict.
 
50 students will be randomly selected from one or two classes in the included schools and they must fulfil all the inclusion criteria:
 
 - Age between 10-12 years or attending grades 5th-7th - Students, male and female, who are in classes close to where the handwashing stations (Gravit'eau) will be positioned in the school (in Nigeria) - Students must be in the same school for the course of the study (1 year). 
Exclusion criteria Modules 1-4: students must not fulfil any of the following exclusion criteria:
 
 - Refusal to participate by not providing signed consent forms or oral assent - having any medical condition that prevents them from washing their hands - having unexplained intermittent attendance in school (school teachers will be consulted and school's absenteeism records will be checked for that) - will not be at the same school for the course of the study (1 year)

- not meeting the inclusion criteria

Inclusion criteria Module 5:

- Students of the classes included in the study in each included school in Palestine

Exclusion criteria Module 5: Refusal to participate by the student or his/her parents

Inclusion criteria Module 6:

For students:

- Students of the intervention schools
- Students from the 50-student sample selected in each included school

For teachers:

- Aged \geq 18 years old
- Permanent employees in the school
- Teaching one of the classes included in the intervention

Exclusion criteria Module 6: Not providing signed consent form and/or oral assent

Inclusion criteria Module 7:

- The participant needs to be:
 - a) a stakeholder within the community, state, region or country of the intervention whose position is related in any way to WASH in schools
 - b) working in one of the intervention schools. They can be teachers, hygiene technicians or in a leading position of the school.
 - c) Minimum age of 18 years

Exclusion criteria Module 7: Refusals to participate


Measurements and Procedures
	
Different methods across modules will be used to achieve the objectives of this project. These modules will include qualitative and quantitative data approaches in order to enable a triangulation of the overall project results. The following modules will be used in the cRCT and the overall project: (i) Module 1: A combined RANAS and wellbeing survey, (ii) Module 2: Structured handwashing observations, (iii) Module 3: Microbiological analysis of hand rinse samples, (iv) Module 4: Diary approach for pre-defined health outcomes and absenteeism incidence, (v) Module 5: personal, physical, and social contextual factor survey, (vi) Module 6:FGDs and (vii) Module 7: Key informant interviews (KII).
 
Endpoints of Modules 1-3 will be assessed at baseline, at follow-up and endline of the cRCT. Module 4 will be used to collect data longitudinally over the course of 12 months. Module 5 will be assessed at baseline and only in Palestine, Module 6 and 7 will be used in the middle of the intervention phase in the intervention groups.

Number of Participants with Rationale (if no Power Analysis conducted)
	
The sample size calculation yielded that 13 schools are needed per arm with 50 students per school. With political instability and other factors which might lead to a loss of follow-up, we have 7 schools as backup schools. This will lead to 26 schools in total with a total number of 1300 students. The number of students participating in different modules will differ due to the capacity limitation of assessing the 50 students included in each school. For module 1, only 25 students of the 50 students included in the study in each school. For module 2, the 50 students included in the study in each school will be targeted for assessment using this module. For Module 3, 12 students out of the 25 randomly selected students to be targeted with RANAS and well-being survey will be targeted for assessment using this module.

	
Module 4 follows the sample size calculation of the cRCT design, hence 50 students from each of the 26 schools will be monitored. For Module 5, all students in the included classes in each school in Palestine will be delivered a survey to be self-reported by their parents. For Module 6, 10 FGDs (including students) and 5 FGDs (including teachers) will be administered and for Module 7, 10-20 interviews.

Study Duration	14 months
Study Schedule	
For Nigeria: May 2023 of First-Participant-In July 2024 of Last-Participant-Out
 
For Palestine: March 2023 of First-Participant-In May 2024 of Last-Participant-Out

Investigator(s)	
[name]. [name] Swiss Tropical and Public Health Institute [name] [contact] [contact]
 
PhD candidate (research assistant) under supervision of [name]. [name]: [name] Swiss Tropical and Public Health Institute [name], Switzerland [contact]
 
[name] Terre des hommes Nigeria [name] [contact], [name] [contact]
 
[name] Project coordinator Cesvi Palestine [name] [name] [contact]
 
[name] Junior Programme Officer Skat Foundation [name] [contact] [contact]

Study Centre(s)	Nigeria and Palestine
Statistical Analysis incl. Power Analysis	The number of clusters (schools) and students per school were calculated using the software R with a power simulation of 80% developed by [name]. The Intraclass Correlation Coefficient (ICC) was assumed at 0.2. The simulation assumed a prevalence of handwashing occurrence before eating during the time of observation (3 hours) taking place over one day of 20% in control vs 45% in intervention schools after 1 year from the

	
baseline. Based on this assumption, 13 schools are needed per arm with 50 students per school.
 
The baseline data will be reported descriptively. The imbalance at baseline between trial arms will be assessed in terms of clinical importance rather than in terms of statistical significance. The intervention effect will be estimated with logistic mixed effect regression to adjust for potential correlation within schools. For the primary analysis, the model will include only the outcome (handwashing occurrence before eating during the time of observation (3 hours) taking place over one day and assessed at the endline) and the intervention as a predictor and school as a random effect. Further analyses will include known confounders and variables imbalanced at baseline. All analyses will use the available case population. No imputation of missing data will be done because loss to follow-up is usually small to moderate in school-based studies.


Ethical consideration
	
This project will be carried out in accordance with the research plan outlined in this protocol and with principles enunciated in the current version of the Declaration of Helsinki / Essentials of Good Epidemiological Practice issued by Public Health Switzerland (EGEP) / ISO EN 14155 / CIOMS International Ethical Guidelines for epidemiological studies 2009 as well as all national legal requirements and guidelines as applicable. This protocol will be reviewed by the Ethikkommission Nordwest- und Zentralschweiz (EKNZ, Ethics Committee of Northern and Central Switzerland) and also be reviewed and approved by the National Health Research Ethics Committee. This trial will be registered at the U.S. National Library of Medicine under https://www.clinicaltrials.gov.

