3.2 Scientific justification of study population

The schools' teachers and students are at increased risk for disease transmission, particularly during disease outbreaks (Wolf *et al.* 2018). Improved water access and hand hygiene are essential to maintaining a hygienic environment for controlling infectious disease transmission in schools (Robinson 2001). In addition, schools are well positioned in principle to implement equitable and sustainable health-related behaviour changes that track from childhood to adulthood (Moore *et al.* 2015).

In Nigeria, it was reported that 70% of the schools lack hygiene services and 43% of them lack sanitation services (UNICEF & WHO 2022). A recent study also showed that there is a significant WASH inequality between private and public schools in Nigeria (Wada *et al.* 2022). None of the public schools included in the study (5 schools) provided any sanitation or hygiene services whereas the other 5 private schools provided both services. The authors of the study indicated that there is a need for sustainable WASH interventions engaging local community stakeholders to facilitate the narrowing of existing inequalities (Wada *et al.* 2022).

The overcrowding conditions in the schools where the average number of students per elementary class ranged from 51 to 101, along with the humanitarian crisis urge the need for targeting these schools with sustainable interventions promoting WASH services and hand hygiene. The targeted schools in H4H project lie around Maiduguri, the capital and the largest city of Borno State in north-eastern Nigeria. The humanitarian needs are increasing in all locations in Borno state due to escalating crisis between the Boko Haram group and the Nigerian army, however, many places like the Mafa refugee camp are hardly or not accessible due to deteriorated security. The focus has been shifted to the schools around Maiduguri, which are likely to remain accessible.

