4 STUDY DESIGN

The overall project will follow a multi-center cluster-randomized controlled trial (cRCT) design (Figure 2). Prior to this study, a group of schools in the study's target areas were surveyed by the Tdh (in Nigeria) and Cesvi (in Palestine) using the Facility Evaluation Tool for WASH in Schools ([FACET WINS](#)) which is a monitoring tool for WASH delivery services in schools. From these schools a subsample was identified which fulfils certain inclusion criteria (for the inclusion criteria see chapter 5.2 Inclusion criteria).

This subsample was handed over to the local Tdh and Cesvi collaborators who carefully assessed the security situation around the schools. The Tdh and Cesvi collaborators then selected 26 facilities per country, which are most probable to still be accessible for data collection within the next year. These 26 schools will then be allocated to the two arms (intervention vs. control) with covariate constrained stratified randomization using computer-generated randomization code provided by a statistician not involved in any field activities. The intervention arm will receive the full intervention package (handwashing station, behavioural change intervention, capacity development, and management support). The control arm will receive nothing for the duration of the intervention (12 months). Afterwards, they will receive the same intervention package with potential improvements identified in the former intervention group.

In the selected schools, 50 eligible students from each school will be selected from one or two classes within the age group (10-12 years) using random sampling. If the school has at least one class that has ≥ 50 students within the target age group, the sample will be selected from that class, otherwise, the sample can be selected from two classes. For module 1, only 25 students of the 50 students included in the study in each school will be involved. For module 2, the 50 students included in the study in each school will be targeted for assessment using this module. For Module 3, 12 students out of the 25 students targeted with assessment using module 1 will be targeted for assessment using this module.

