The study design will be baseline cross-sectional. This objective will be fulfilled through the baseline assessment conducted before randomising the recruited schools in Palestine into the two arms of the study. The assessment will be carried out through a survey that is self-reported by the parents of the students in the selected classes for the study. The survey will include questions related to the availability of hygiene services at the household level, evaluation of parents' hygiene knowledge and behaviour, and assessment of their child's hygiene behaviour as reported by them.

Module 6: Focus Group Discussions: The FGD is a rapid and resource-efficient method of gathering information since all the target participants and the researcher are readily available at the same study site (Mack *et al.* 2005; Nyumba *et al.* 2018). There is no need to collect participants from different environments and prepare them in advance, rather, they will be met in their usual studying environment which also helps not to introduce their expectations and biases, including strategic group bias (Nyumba *et al.* 2018). Also, the concentrated nature of the FGD avails a large quantity of data in much less time usually needed to collect an equivalent number of interviews (Nyumba *et al.* 2018).

10 gender-separated FGDs will take place in the included schools in the intervention arm; 5 FGDs for each gender in autumn 2023. However, the saturation factor⁶ will be considered when conducting the discussions in the field. Each group will include students of the same age of the age group target (10-12) to avoid any domination of older students if the groups include different age groups. Using separate groups for boys and girls will help ensure meaningful feedback since children may feel shy speaking in front of each other and usually there is an increase in teasing among children at the age of 10 (Dzino-Silajdzic 2018). It is important for them to feel comfortable speaking their minds freely and not feel shy, embarrassed or worried someone will make fun of them (Dzino-Silajdzic 2018). Each FGD will be composed of 5-8 selected students. The selection of the students will be consulted with the school administration, however, selected students need to represent each participating class in the intervention arm of the trial.

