5.2 Inclusion criteria

Study participants will be primary school students of schools selected to be included in this study. Schools were selected based on accessibility for the study teams, not having a water source directly connected to the building of the school, having \leq 7000 students. 50 students within the age of 10-12 years old from one or two classes (depending on the number of students in classes) of the 5th-7th grades will be included in the study from each included school. However, due to the large size of the schools and high number of classes in Nigeria, the 50 students will be selected from two classes of the 5th-7th grades close to where the handwashing stations (Gravit'eau) will be positioned. The 50 selected students will be targeted with the handwashing observation (Module 2) and followed for their hygiene-related health outcomes and absenteeism during the course of the study (Module 4), while 25 of them will be targeted with RANAS and well-being survey (Module 1) and 12 of them will be targeted with collecting their hand-rinse samples (Module 3). Students in the selected classes in each school will be delivered a survey to be self-reported by one of their parents about contextual factors that could affect hygiene practice of students (Module 5 in Palestine only).

Inclusion criteria Modules 1-4: students must fulfil all the inclusion criteria:

- Primary school students aged 10-12 years attending included schools
- Students must be in the same school for the course of the study (1 year).

Inclusion criteria Module 5: students must fulfil all the inclusion criteria:

- Students of the classes included in the study in each included school in Palestine

Inclusion criteria Module 6:

- Students of the intervention schools
- Students need to represent each included class in the intervention.

The teachers invited to participate in the FGDs should be

- Aged \geq 18 years old
- Permanent employees in the school
- Teaching one of the classes included in the intervention

Inclusion criteria Module 7:

- The participant needs to be:
 - a) a stakeholder within the community, state, or region of the intervention whose position is related in any way to WASH in schools
 - b) working in one of the intervention schools. They can be hygiene technicians, teachers, school's principal, or in a leading position in the school.
- Aged \geq 18 years old

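### In Nigeria, pupils in both arms qualify by nearness to a planned station site, and the readable text does not fix site, classes and pupils before allocation

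*Combined protocol and SAP*

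**What the plan says.** The Synopsis criteria for Modules 1-4 require that Nigerian pupils be those "who are in classes close to where the handwashing stations" are to be placed. Section 5.2 gives a practical reason (large schools with many classes) and says that "the 50 students will be selected from two classes of the 5th-7th grades close to where the handwashing stations (Gravit'eau) will be positioned". Neither place distinguishes the arms or defines closeness. The bulleted criteria in Section 5.2 leave nearness out.

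On the control arm, Section 4 says: "The control arm will receive nothing for the duration of the intervention (12 months"). The next sentence promises these schools the same package afterwards, and Section 9.2 confirms it.

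Section 4 also has a general class rule without nearness. If one class holds at least 50 pupils of the target age, "the sample will be selected from that class, otherwise, the sample can be selected from two classes".

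On timing, Section 4 describes the allocation of schools first and the selection of pupils in the next paragraph. Under Module 1 it puts the baseline survey before the intervention package. Under Module 5, which runs only in Palestine, it says the baseline is "conducted before randomising the recruited schools in Palestine into the two arms of the study". Section 4.3 says that participants, data collectors and the statistician cannot be blinded; only the laboratory staff counting colonies are.

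**The concern.** In a cluster trial, randomisation balances schools. It does not balance what is done inside a school once the arm is known. If a Nigerian team picks classes after allocation, an intervention school has a real installation to measure from, while a control school has a site that may not yet have been chosen. Two teams following the same words could then select different kinds of classes, for example by grade or by distance from existing water. Drawing the 50 pupils at random within the chosen classes does not repair this. Nor does the primary model in Section 6.3, which has no baseline outcome, class or distance term.

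The second issue concerns scope. The primary objective (Section 3.1.2) and hypothesis (Section 6.1.1) speak of primary school pupils in the two countries. The Nigerian data will come only from classes near the station, or near its planned site in control schools.

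**Working it through.** **1. The plan's own figure.** Inputs from Section 6.2: 20% versus 45%, 80% power, 95% confidence (read as two-sided 0.05), ICC 0.2, 50 pupils per school.
- Without clustering, with mean proportion 0.325: n = [1.96·√(2·0.325·0.675) + 0.84·√(0.20·0.80 + 0.45·0.55)]² / 0.25² ≈ 54 per arm.
- Design effect: 1 + (50 − 1)·0.2 = 10.8.
- Schools per arm: 54·10.8/50 = 11.66. Adding one for the small number of clusters gives 12.66, rounded up to 13.

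The stated 13 is reproduced. Simulation (beta-binomial, t-test on school proportions) gives 82% power at 13 schools per arm and 79% at 12. The present point does not change the sample size.

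**2. What is fixed, and when.**
- *Criterion:* one rule for all Nigerian schools, worded in the future tense (Synopsis, 5.2).
- *Reference point in control schools:* a later installation (4, 9.2), so a planned site is meaningful. No text says how or when it is set.
- *Order:* allocation is described before pupil selection (4). This is the order of description and does not prove the order of events.
- *Who chooses:* no text assigns the choice of classes to someone unaware of the arm, and field staff are unblinded (4.3).
- *Adjustment:* none in the primary model (6.3). Terms for variables imbalanced at baseline enter only in the secondary analysis (6.3.1.2).

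**3. What a difference in class selection would do.** The documents give no figure for such a difference, so the offsets here are assumptions. Setting: 13 schools of 50 per arm, ICC 0.2, two-sided test at 0.05, and every school in the comparison subject to the nearness rule.
- No true effect, with the selected intervention classes having an underlying rate higher by 0, 5, 10 or 15 points than the selected control classes: rejection rate 4.9%, 9.7%, 23.7%, 43.7%.
- Intervention at 45%, with the selected control classes at 20%, 25%, 30% or 35%: power 82%, 62%, 38%, 19%.

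The direction is therefore open. If Palestinian schools are pooled in, the shift shrinks in proportion to the Nigerian share of schools.

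**4. How narrow the sampled group is.** Section 3.2 reports that "the average number of students per elementary class ranged from 51 to 101", and Section 5.2 admits schools of up to 7000 pupils.
- Two classes hold 2·51 = 102 to 2·101 = 202 pupils.
- In a school at the ceiling this is 102/7000 = 1.5% to 202/7000 = 2.9%. Smaller schools have a larger share, and typical school size is not given.
- Suppose nearby pupils rise by 25 points and the others by none (assumed). The school-wide difference is then share × 25: 2.5, 6.3 or 12.5 points if nearby pupils are 10%, 25% or 50% of the school.
- If the others rise by 10 points (assumed), it is share × 25 + (1 − share) × 10: 11.5, 13.8 or 17.5 points.

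**The case against.** The strongest reply is that one rule, in the future tense, applies to every Nigerian school, and control schools do have a future site because they receive the package later. That stands. A reader might infer that the criterion has no meaning in a control school, and the documents do not support that.

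Next, being near a new station is part of what the intervention delivers. Intervention pupils having a station close by while control pupils have only existing water points is the treatment contrast, not selection bias. That also stands: bias arises only if the classes themselves are chosen differently by arm.

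A reader might also take the statement that baseline precedes randomisation in Palestine as a sign that Nigeria does the reverse. It is weak evidence, since Module 5 exists only in Palestine. The flow diagram for Nigerian schools and the cells of the schedule cannot be read in the available text and may hold the answer.

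The one-class and two-class rules may look contradictory. Section 5.2 reads as a reasoned exception for Nigeria. The 51 to 101 figure is whole class size, whereas the Section 4 threshold counts only pupils of the target age, so the figure does not show how often one class would suffice. What is missing is a cross-reference.

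Finally, handwashing is observed at baseline and adjusted analyses are planned, so a large class difference could be seen. This helps, but the adjustment is secondary, and the restriction to nearby classes is unaffected by it.

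**Conclusion.** The point holds as an unprotected step in the design. In Nigeria, the choice of classes within schools is not stated to precede allocation, is made by staff who may know the arm, and is not corrected in the primary model. A reader might go further and conclude that the arms do differ or that the primary result is biased. The documents do not show that. If sites, classes and pupils were in fact fixed in every Nigerian school beforehand, the comparison is protected and only the wording is at fault.

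The size of any bias cannot be derived from the plan. The error rates and power values above show sensitivity to assumed offsets and are not estimates. The limit on scope does not depend on those offsets: however the arms are selected, the Nigerian estimate describes pupils in classes near the station or its planned site. How far it departs from a school-wide effect depends on the share of nearby pupils and the gain among the others, neither of which is given. The change should be made because the safeguard is concrete and costs little.

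**What to change.** - **Synopsis, Section 4 and Section 5.2:** require that in every Nigerian school, in both arms, the planned station site is set by one common siting rule, the nearest classes are listed, and the 50 pupils are drawn before the allocation is released.
- **If pupils are already enrolled:** document when and how the control classes were chosen, and report baseline handwashing by arm.
- **Consistency:** cross-refer the class rule in Section 4 to the Nigerian two-class exception in Section 5.2, and add nearness to the bulleted criteria there.
- **Scope:** state, alongside Sections 3.1.2 and 6.1.1, that the Nigerian estimate applies to pupils in classes near the station or its planned site.

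The cost is protocol wording, siting all Nigerian schools at the start instead of only the intervention schools, and a narrower stated conclusion. The sample size and the primary model stay as they are.
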